3.1.2.1.1 Thin, white, yellow, homogeneous discharge

3.1.2.1.2 Clue cells on wet mount microscopy

3.1.2.1.3 a vaginal fluid pH of over 4.5 when placing the discharge on litmus paper

3.1.2.1.4 Release of fishy odor when adding 10% potassium hydroxide (KOH) solution to wet mount - also known as “whiff test.”

3.1.3 Safety: adverse events via MedDRA criteria.

3.2 Secondary Outcome Measures Time to recurrence measured by failure rates and time-to-failure. Defined by Amsel's criteria or by Nugent criteria (gram stain results). To be measured at visit 2 (3-5 days after initial treatment), visits 3-6 (week 6, 10, 14, and 18 during suppressive treatment), visits 7 & 8 (22 & 30 weeks after initiation of treatment).

3.3 Tertiary/Exploratory/Correlative Outcome Measures Participant compliance, tolerance, and adverse event data to be collected via a patient questionnaire at each visit. The safety of secnidazole was evaluated in five Phase 1 clinical trials before FDA approval. The five most common treatment-associated adverse events were: vulvovaginal candidiasis, headache, nausea, diarrhea, abdominal pain, and vulvovaginal pruritis. We will monitor for the frequency and severity of these events and any other subject-related side effects.

4. Eligibility Criteria

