4.2 Exclusion Criteria

[figure not shown]
- Current gynecologic infection or condition, including candida vaginitis, gonorrhea, chlamydia, trichomonas, desquamative inflammatory vaginitis, atrophic vaginitis.
- Pre-existing heart conditions
- Pre-existing neurological conditions
- Currently Pregnant or breastfeeding
- Women taking anticoagulants, lithium, metoclopramide, or disulfiram therapy
- Hypersensitivity to secnidazole or other drugs in the same class.

5. Study Design

A single-center prospective pilot study with once-weekly oral secnidazole granule treatment of an acute condition for two weeks followed by prophylactic treatment of asymptomatic responders with once-weekly secnidazole for 16 weeks, followed by no therapy for 12 weeks. The final follow-up evaluation is at week 30.

Eligible women with a current symptomatic bacterial vaginosis infection (\geq 3 Amsel criteria) and a history of at least 2 previous episodes of bacterial vaginosis in the past year will be enrolled in the open-label treatment study. All women will be treated with 2g of secnidazole granules orally once weekly for 2 weeks. At the second visit, 3-5 days after completion of treatment, women who have a clinical resolution of bacterial vaginosis (asymptomatic and \leq 2 Amsel criteria, will also be reported as asymptomatic and $<$ 1 Amsel criteria) will continue on once-weekly secnidazole for 16 weeks.

Patients will be evaluated at week 6, 10, 14, and 18 for recurrence of bacterial vaginosis. This will include questions about symptoms as well as a pelvic examination for assessment of vaginal discharge (\geq 3 Amsel criteria). We will also collect any information on other clinical evaluations for recurrence and the dates of diagnoses and types of treatments they may have received. Those who remain without recurrence during the 16-week suppressive phase will be followed for an additional 12 weeks off therapy, with assessment for recurrence at weeks 22 and 30. Throughout the study, data will be collected on participants' compliance and on the occurrence of adverse events.

6. Enrollment

Participants presenting to the IU Coleman Center with a history of recurrent bacterial vaginosis who are currently symptomatic will be evaluated for enrollment in the study. Informed consent will be obtained.

7. Study Procedures

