At each visit where women are evaluated for BV they will be asked about vaginal discharge. Then they will undergo a speculum examination of the vagina similar to pelvic examinations performed clinically at most annual gynecologic examinations. Any vaginal discharge present will be collected by a swab for assessment of pH, odor, and presence of clue cells on microscopy. The speculum examination should take ~2 minutes.

At the initial enrollment visit, subjects will be given a point-of-care pregnancy test. If the test is positive, the subject will not be placed on study drug, and will receive alternate, traditional suppressive therapy. Women enrolled will be instructed in the use of the secnidazole granules by trained study personnel or the medical provider. If a subject becomes pregnant during the study, we will terminate study drug for the subject and follow the subject for any adverse pregnancy outcomes for safety reporting. The subject will have a basic neurological test at enrollment.

At follow up visits, women will again be queried about vaginal discharge and will undergo a speculum examination as above, even if they do not endorse vaginal discharge. Subject will have a basic neurological test at follow up visits.

Women will be asked about any adverse side effects of the secnidazole including vaginal irritation, bleeding, redness, or itching. If the subject presents with vulvovaginal candidiasis, they will be treated with oral or vaginal fluconazole, per patient preference, if they present to the PI, or with the standard of care if they present elsewhere. The treatment will be noted.

If the subject or potential subject has any history of heart disease or disorders of the heart, they will be excluded from participation.

If a study participant has recurrence of bacterial vaginosis while on protocol, the subject will fail study treatment, and will be placed on alternate, traditional suppressive therapy. The participant will have completed the study at this point.

8. Study Calendar

Event/Procedure	Treatment						Follow Up		Unscheduled
	Enrollment/V1 Day 1	V2 Day 18	V3 Week 6	V4 Week 10	V5 Week 14	V6 Week 18	V7 Week 22	V8 Week 30	
Window		+/- 1 day	+/- 5 days						
Screening	x								
Confirm eligibility	x								
Informed consent	x								
Collection of MHx	x								
Symptom Assessment	x	x	x	x	x	x	x	x	x
Pelvic Exam	x	x	x	x	x	x	x	x	Per SOC
STI Testing	SOC								Per SOC
Whiff test	x	x	x	x	x	x	x	x	Per SOC
Vaginal pH	x	x	x	x	x	x	x	x	Per SOC

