Wet mount	x	x	x	x	x	x	x	x	Per SOC
Gram stain	x	x	x	x	x	x	x	x	Per SOC
Study Drug Administration	x	x*	x*	x*	x*	x*			
Med compliance assessment			x	x	x	x			

*study drug provided to asymptomatic subjects only at V2 - V6.

9. Reportable Events

The study is expected to be only slightly greater than minimal risk as the study medications and examinations are those that are commonly used during routine clinical care and evaluations. Secnidazole (study drug) has FDA approval for the treatment of acute BV with minimal side effects reported.

Any severe adverse effects including unexpected hospitalization due to treatment will be reported per IRB guidelines. Any non-severe Adverse Events (“AE”s) such as sensitivity or side effects will be reported in aggregate at annual reviews. Expected/common side effects of the examinations are discomfort and irritation. There is a minimal risk of vaginal bleeding. Side effects reported with secnidazole include vulvovaginal candidiasis, headache, mild gastrointestinal discomfort, and vaginal itching.

An adverse event (“AE”) is defined as any untoward medical occurrence associated with the use of a drug in humans, whether or not the event is considered drug-related. An AE can therefore be any unfavorable and unintended sign (including an abnormal laboratory finding that is unrelated to the intent of the study), symptom, or disease temporally associated with the use of a drug. An adverse reaction means any adverse event caused by a drug. Adverse reactions are a subset of all suspected adverse reactions for which there is reason to conclude that the drug caused the event. A suspected adverse reaction implies a lesser degree of certainty about causality than an adverse reaction.

Pre-existing conditions are not considered adverse events unless there is an unexpected change in the frequency, intensity, or nature of the condition. A newly diagnosed pregnancy during study enrollment will not be considered an adverse event. If a pregnancy occurs during the treatment or maintenance phases of the study, the subject will be asked to discontinue the study drug and be terminated from the study.

Pregnancy reports:

Pregnancy reports of subjects should be forwarded to Lupin Research Inc. This also includes normal pregnancies without AE. If a pregnancy occurs during the treatment or maintenance phases of the study, the subject will be asked to discontinue study drug and be terminated from the study.

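### Study drug must stop if pregnancy occurs, but the only pregnancy test described is at enrollment, and no later check is described before drug is supplied at V2 to V6

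*Protocol*

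**What the plan says.** The trial enrolls women aged 18 to 50 (Protocol Section 4.1) and excludes those who are pregnant or breastfeeding at entry (Section 4.2).

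On testing, Section 7 says: "At the initial enrollment visit, subjects will be given a point-of-care pregnancy test". A positive result means no study drug.

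On pregnancy arising later, Section 7 says: "If a subject becomes pregnant during the study, we will terminate study drug for the subject". Section 9 repeats the rule: "If a pregnancy occurs during the treatment or maintenance phases of the study, the subject will be asked to discontinue the study drug". It also ends her participation and requires the pregnancy to be reported and followed to its outcome, including any birth defect.

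For follow-up visits, Section 7 describes a discharge query, a speculum examination and side-effect questions. It repeats one enrollment safety check by name: "Subject will have a basic neurological test at follow up visits". It does not repeat the pregnancy test.

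The Section 8 footnote on supply reads: "study drug provided to asymptomatic subjects only at V2 - V6". Section 5 adds the limit of at most 2 Amsel criteria at V2, and Section 7 ends participation on recurrence.

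Section 3.3 describes a questionnaire: "Participant compliance, tolerance, and adverse event data to be collected via a patient questionnaire at each visit". Section 9 says of pregnancy: "A newly diagnosed pregnancy during study enrollment will not be considered an adverse event". The SAP does not mention pregnancy.

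**The concern.** The protocol treats pregnancy as a reason to stop drug, end participation and follow the woman to outcome, but describes no step after enrollment that would reveal a pregnancy she does not yet know about. Followed as written, a woman who is free of vaginosis symptoms and has an unrecognised pregnancy would receive more drug, although she attends the site about every four weeks and the site already uses a point-of-care test.

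This is a participant-safety point, judged by the protocol's own stop rule. The documents give no fetal-risk figure and no pregnancy rate, so neither is assumed. They do say that secnidazole has not been studied for suppression and that its approval is for acute disease, so routine use cannot be taken to cover this length of dosing.

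**Working it through.** **1. Possible routes to detecting a pregnancy after V1**

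| Route | Where | Would it find an unrecognised pregnancy? |
|---|---|---|
| Point-of-care test | Section 7 | Yes, but described at enrollment only |
| Follow-up procedures | Section 7 | No pregnancy check described |
| Eligibility confirmation, medical history | Section 8 calendar | Both rows marked at V1 only |
| Supply conditions | Sections 5, 7, 8 | No; they concern vaginosis |
| Questionnaire at each visit | Section 3.3 | Stated scope is compliance, tolerance and adverse events; Section 9 says pregnancy is not an adverse event |
| Self-report and record review | Section 13 | Only a pregnancy already known |

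**2. Doses after the V1 test, nominal visit days**

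Inputs: 2 acute weekly doses, then weekly dosing for 16 weeks (Section 5); V2 on Day 18, V3 to V6 at Weeks 6, 10, 14 and 18 (Section 8). Assumptions: week w is Day 7w, suppressive dosing starts on the V2 day, and any check comes before that day's dose.

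- Suppressive doses fall on Day 18 + 7k for k = 0 to 15, that is Days 18, 25, ..., 123: 16 doses.
- All doses: 2 + 16 = 18, so 16 of 18 are supplied from V2 on.
- Visits fall on Days 18, 42, 70, 98 and 126.
- V2 to V3: Days 18, 25, 32, 39 = 4 doses.
- V3 to V4: Days 46, 53, 60, 67 = 4.
- V4 to V5: Days 74, 81, 88, 95 = 4.
- V5 to V6: Days 102, 109, 116, 123 = 4.

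**3. The same count with visit windows**

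The window is 1 day either side at V2; the 5-day window is read as applying from V3 on. V2 is then Day 17–19, V3 Day 37–47, V4 Day 65–75, V5 Day 93–103 and V6 Day 121–131.

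| Interval | Fewest doses | Most doses |
|---|---|---|
| V2 to V3 | 3 | 5 |
| V3 to V4 | 2 | 6 |
| V4 to V5 | 2 | 6 |
| V5 to V6 | 2 | 5 |

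Example of 6: V2 on Day 18, V3 on Day 37, V4 on Day 75 leaves doses on Days 39, 46, 53, 60, 67 and 74.

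V6: if the last dose is due on Day 123, one dose remains only if V6 is held on Days 121–123.

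**4. Number of tests**

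Section 12 works with 42 of 50 women after early loss.

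- V2 to V5: 42 × 4 = 168; if all 50 continued, 50 × 4 = 200.
- With V6 as well: 42 × 5 = 210; if all 50 continued, 50 × 5 = 250.

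Within each line these are upper bounds, because women unresolved at V2 or with recurrence leave the study.

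**The case against.** The best counter-argument is that this is an argument from silence. The calendar is incomplete: it omits the V1 pregnancy test and the neurological tests. The Section 7 follow-up text is incomplete too: it omits the Gram stain and the compliance assessment. That stands as a caution. The enrollment test is nevertheless described, the neurological test is expressly repeated at follow-up, and a repeat pregnancy test appears nowhere.

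Three stronger readings are tempting, and the documents do not support them.

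- A reader might infer from the calendar footnote that being asymptomatic is the only condition for supply. It is not. The Amsel limit at V2, recurrence and a known pregnancy also bar supply. The gap is confined to unrecognised pregnancy.
- A reader might infer that women are never asked about pregnancy. The questionnaire items are not shown and could include such a question, and the site must collect pregnancy reports somehow. It can be said only that none is described.
- A reader might take the contrast as a cap of 6 doses against a typical 16. Sixteen is a worst case: it needs a pregnancy to stay unrecognised from Day 18 to Day 123, which is 105 days or 15 weeks. Six is not a ceiling, because a test that misses an early pregnancy lets exposure run past the next check.

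It can also be said that the stop rule does not itself require a test at every dispensing, that V2 comes only 17 days after the V1 test, and that the protocol rates the study as only slightly above minimal risk. A question about missed periods, with a test when indicated, would be a lighter alternative. It would depend on the woman's own suspicion, whereas a test does not. A V2 test may miss a recent conception, but it gives a second chance to find a pregnancy too early to show at V1.

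**Conclusion.** The concern holds in a limited form. Sections 7 and 9 require drug to stop on pregnancy, the only test described is at enrollment, and no later test or targeted question is described before supply at V2 to V6. The stop, reporting and follow-up rules are sound; what is missing is a scheduled way to trigger them when the woman does not know she is pregnant.

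Size: at worst, 16 suppressive doses without a scheduled check, against about 4 between checks (2 to 6 with windows) if she is tested at each dispensing. This rests on weekly dosing from the V2 day and on the reading of the visit windows given above. The number of women affected cannot be estimated, and no endpoint or estimate is redefined. The sponsor should make the change because it is cheap and serves the protocol's own rule. Confidence is medium, because the questionnaire items cannot be seen.

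**What to change.** In Section 7, repeat the point-of-care pregnancy test before each dispensing from V2 on: V2 to V5, and V6 if drug is dispensed there. Withhold drug if the test is positive, under the existing rule in Sections 7 and 9. In Section 8, add a pregnancy-test row marked at V1 and at these visits.

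The cost is a short amendment and about four low-cost tests per continuing woman: at most about 168 for 42 women, or 250 if all 50 continued and V6 also dispenses. No new visits, staff or invasive procedures are needed. The downside is that a few women may leave suppression. The SAP is written in the past tense; if dosing has finished, the change belongs in the larger comparative trial that this pilot is meant to inform.

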The pregnancy should be followed up to determine outcome, including spontaneous or voluntary termination, details of birth, and presence or absence of any birth defect, congenital abnormalities or maternal and newborn complications. Pregnancy follow-up should be conducted until the outcome.

The pregnancy reporting procedure should be the same as the Serious AE reporting procedure set out in Section 2.7 of the Agreement.

Additional Notes on Adverse Events and Serious Adverse Events:

For the purposes of this study, changes in clinical criteria (i.e. Amsel criteria and/or symptoms) from baseline that are associated with BV will be captured on the corresponding case report forms and should not be recorded as an adverse event with the following exception:

- If in the investigator/clinician's opinion a subject treated for BV gets a secondary infection (e.g. yeast infection), the yeast infection should be captured as an adverse event.

Each AE or suspected adverse reaction must be assessed for its seriousness. The term "serious" is not synonymous with "severe" that may be used to describe the intensity of an event or reaction. An AE or suspected adverse reaction is considered serious if in the view of either the investigator:

- Results in death
- Is life threatening (referring to an adverse event or suspected adverse reaction in which either the investigator or the sponsor believes the subject was at risk of death at the time of the event or reaction; it does not refer to an event that hypothetically might have caused death if it were more severe).
- Requires inpatient hospitalization or prolongs an existing hospitalization
- Results in a persistent or significant disability/incapacity
- Is considered medically important

Important medical events are those that may not be immediately life threatening but are of major clinical significance and may require intervention to prevent one of the other serious outcomes listed above. Examples include a seizure that did not require in-subject hospitalization or allergic bronchospasm that needed emergency treatment.

All adverse events or suspected adverse reactions that do not meet the criteria for serious will be regarded as non-serious.

Definition of Unexpectedness: An adverse event or suspected adverse reaction is considered unexpected if the nature/specificity or severity of the event or reaction is not consistent with applicable product information.

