Documentation of Adverse Events: All adverse events (serious and non-serious) that occur from the time informed consent is signed through Visit 8 must be reported and recorded in source documentation and the appropriate page(s) of the CRF. Information to be documented for each AE includes the following:

- Adverse event term
- Severity of the event (mild, moderate, or severe)
- Start and stop date (if applicable)
- Time of the event if it occurred on the first day of study drug administration
- Relationship to study drug (none, possible, probable, definite)
- Action taken with the study drug (none, study drug interrupted, study drug discontinued)
- Action taken (none, new medication/treatment, termination from study, hospitalization, other)
- Outcome of the event (resolved, resolved with sequelae, ongoing, death, or unknown)
- Whether or not the event meets serious criteria.

If AE signs and symptoms are the result of a specific diagnosis, the diagnosis only (and not the cluster of signs and symptoms that make up the diagnosis) should be reported on the CRF.

Severity criteria: Severity criteria for adverse events will be defined as follows:

- Mild: awareness of signs/symptoms that are easily tolerated causing minimal discomfort and not interfering with normal daily activities
- Moderate: Sufficient discomfort is present and may interfere with normal daily activities
- Severe: Extreme distress is present causing significant impairment of functioning or incapacitation preventing normal daily activities.

The investigator should use clinical judgement in assessing the intensity of adverse events not directly experienced by the subject (e.g., lab abnormalities).

Relatedness Criteria: An adverse event is considered associated with the use of the drug if the attribution is possible, probable, or definite. Attribution definitions for the relatedness of adverse events will be defined as follows:

- None: An adverse event that is not related to the use of study drug.

- Possible: An adverse event that might be due to the use of the drug; an alternative explanation (e.g. a concomitant drug or illness) is inconclusive. The relationship to time is reasonable.
- Probable: An adverse event that might be due to the use of the drug; an alternative explanation (e.g. a concomitant drug or illness) is less likely. The relationship in time is suggestive.

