As this is a pilot project to determine the rates of recurrence with this therapy, no a priori sample size was calculated. We aim to recruit 50 women to determine this rate. That is a similar sample size to other studies in this area. The rates determined by this pilot study will be used in sample size calculations for a larger comparative trial. If the patient population behaves similarly to other BV studies, this study can expect to lose 15% immediately after enrollment as a loss to follow-up. In similar studies, 25.5% had recurrence of BV at the end of the 16-week maintenance phase. A total of 51% had recurrence of BV by the end of the 28-week follow-up phase. In a 50-subject trial, if secnidazole has a similar performance, this would yield approximately 21 subjects that have resolved symptoms through the full 30 weeks of participation.⁷ For this pilot study, we anticipate this 50% symptom resolution rate \pm 15%. In consideration of this, $21/42 = 0.50$ with 95% CI of 0.34 to 0.66 (exact) at 30 weeks, the half-width would be 0.16. We will report rates as point estimates and 95% confidence intervals. For proportions/rates, we will use exact binomial confidence intervals, and, for time to event, we will estimate the confidence intervals using the Kaplan-Meier method.

13. Statistical Data Management

Primary data will be collected via subject self-report and EMR review and stored electronically in REDCap electronic CRF. A backup of the CRF data in REDCap will be saved on a nightly basis to a secure environment maintained by the Research Technologies division of University Information Technology Services (UITs)..

- Quality assurance steps will include:
 - Testing of database prior to being placed into production mode
 - Automated range checks.
 - Manual verification of any self-reported subject data; clinical notes/ electronic medical chart will take precedence over self-reported data, except when overridden by PI or their designee.
 - Single entry with random checks of accuracy and extraction and cleaning of data that will be used for analysis every 6 months.

14. Privacy/Confidentiality Issues

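### Section 9 requires adverse events to be recorded through Visit 8, but about a quarter of evaluable women would leave at an on-drug recurrence, within about a week of a dose and with no planned safety contact afterwards

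*Protocol*

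**What the plan says.** Protocol Section 9 (Documentation of Adverse Events) covers all adverse events, serious and non-serious, "that occur from the time informed consent is signed through Visit 8 must be reported". Visit 8 is at week 30.

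Section 7 says that a woman whose bacterial vaginosis recurs on protocol fails study treatment and moves to other suppressive therapy. It then adds: "The participant will have completed the study at this point". Section 5 continues only women with clinical resolution at Visit 2, and gives the 12 weeks of off-therapy follow-up only to those without recurrence in the suppressive phase. The Section 8 calendar has no exit visit, no safety contact after the last dose and no adverse-event row. Adverse-event questions are tied to visits (Sections 3.3 and 7).

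For pregnancy, Section 9 says that "the subject will be asked to discontinue the study drug and be terminated from the study", and a little later that "Pregnancy follow-up should be conducted until the outcome". Section 7 also asks for follow-up of a pregnant woman for safety reporting.

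Section 13 names a second data source: "Primary data will be collected via subject self-report and EMR review". The SAP's statistical methods section describes only the efficacy analyses.

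**The concern.** A site cannot follow Sections 7 and 9 as both are written. If it closes a woman's participation at recurrence, it does not collect what Section 9 requires of every participant. If it keeps collecting, it has no visit, contact or stated procedure for doing so.

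The data lost are not a random part of the safety record. A woman who recurs on drug leaves days after a dose. A woman who does not is seen again several weeks after dosing ends. How completely late or persisting events are captured therefore depends on the efficacy outcome. Safety is part of the primary objective (Section 2.1), and the background states that secnidazole has not been studied for suppression of recurrent disease. Neither a different denominator nor an exposure adjustment can recover events that were never recorded.

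**Working it through.** **Inputs, all from Protocol Section 12 unless stated**
- Enrolment: "We aim to recruit 50 women to determine this rate".
- Early loss: "this study can expect to lose 15% immediately after enrollment as a loss to follow-up".
- On-drug recurrence: "25.5% had recurrence of BV at the end of the 16-week maintenance phase".
- Cumulative recurrence by the end of the follow-up phase: 51%.
- Visit times (Section 8): V2 Day 18 +/- 1, V6 week 18 (Day 126), V7 week 22 (Day 154), V8 week 30 (Day 210).

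**Step 1. Reproduce the plan's figure.** 50 x (1 - 0.15) = 42.5 retained; 42.5 x (1 - 0.51) = 20.8, about 21. The exact 95% interval for 21/42 is 0.342 to 0.658, half-width 0.158. This matches the stated 0.34 to 0.66 and 0.16.

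**Step 2. Split the recurrences by phase, using the protocol's 42.**
- On drug: 0.255 x 42 = 10.7, about 11.
- Off drug: (0.51 - 0.255) x 42 = 10.7, about 11.

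Eleven of 42 is 26%, with an exact 95% interval of 14% to 42%. Against all 50 enrolled, 10.7/50 is 21%.

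**Step 3. Time from last dose to exit.** With weekly dosing, a woman who recurs at V3 to V6 is at most about 7 days from her last dose. For women who finish the 16 weekly doses, the gap depends on when those doses start, which the documents do not fix:

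| Assumption | Last dose | To V6 | To V7 | To V8 |
|---|---|---|---|---|
| First of 16 doses on Day 18 | 18 + 15 x 7 = Day 123 | 3 days | 31 days | 87 days |
| First of 16 doses on Day 14 | 14 + 15 x 7 = Day 119 | 7 days | 35 days | 91 days |
| Last dose taken at V6 | Day 126 | 0 days | 28 days | 84 days |

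Off-drug recurrences found at scheduled visits therefore have about 4 to 5 weeks (V7) or 12 to 13 weeks (V8) of observation after the last dose.

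**Step 4. Visit 2 exits.** If the two initial doses fall on Days 1 and 8, V2 is 18 - 8 = 10 days after the last dose (9 to 11 with the window). If completion of treatment in Section 5 means the last dose itself, the gap is the 3 to 5 days stated there. No Visit 2 response rate is planned for the two-dose regimen. As an assumption, take the single-dose response figures in the background and apply 25.5% on-drug recurrence to the responders:

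| Response | V2 exits of 42.5 | On-drug recurrences | Share leaving before the off-drug phase |
|---|---|---|---|
| 93.1% | 2.9 | 10.1 | 31% |
| 90.8% | 3.9 | 9.8 | 32% |
| 73.3% | 11.3 | 7.9 | 45% |

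The 15% early loss may overlap with the V2 exits, so this range is only indicative.

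**Step 5. Who misses part of the Section 9 window.** Among the 42, on-drug recurrences (about 11) always do. Women who recur at V7 miss the last 30 - 22 = 8 weeks. Women diagnosed at V8 miss nothing. The documents give no V7/V8 split, so the count through recurrence lies between about 11 and about 21.

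**The case against.** The strongest reply is that little relevant safety information is lost. Adverse events are asked about at every visit, including the one where recurrence is found, and follow-up visits include a neurological test. Known serious events are followed until resolved or stable. With the half-life of 17 to 29 hours given in the background, five half-lives are 5 x 17/24 = 3.5 to 5 x 29/24 = 6.0 days, so an exit visit up to 7 days after a dose covers part or all of elimination. At about 10 days, a Visit 2 exit is past it. Moreover, a woman who recurs at week 6 would spend 30 - 6 = 24 weeks of the Section 9 window after the switch to other therapy, and late events would be hard to attribute to secnidazole.

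Most of this stands, and it limits the point: the on-drug leavers have a window of days, not none. It does not remove the conflict. Events that persist, or come to notice after exit, are still required by Section 9 and still have no planned route into the record. Poor attribution is a reason to flag late events, not to leave their collection undefined.

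The pregnancy passages can also be read together: participation ends and safety follow-up continues. That is a fair reading, and it leaves only a point of wording.

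**Conclusion.** The passages conflict and should be reconciled. The gap reaches about 11 of 42 evaluable women (25.5%), who would leave during dosing within about a week of a dose, plus an unknown number of Visit 2 exits at a somewhat longer gap. This rests on the cited recurrence rates applying here, on weekly doses taken as scheduled, and on the Day 1 and Day 8 assumption for Visit 2. The loss concerns mainly non-serious events after exit. It does not affect the recurrence estimate.

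A reader might infer from the 51% that about half of the women have no safety window after their last dose, or that about 21 never reach Visit 8. The documents do not support either. Half of those recurrences fall in the off-drug phase and are seen weeks after dosing ends, and a recurrence found at V8 comes with the full window. Nor is post-dose safety seen only in treatment successes, because failures at V7 and V8 contribute to it. A recurrence brought forward to an unscheduled visit soon after week 18 could shorten the interval for a few women.

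**What to change.** Reconcile Sections 7, 8 and 9 by stating two separate end points: the end of efficacy follow-up (recurrence, non-resolution at Visit 2, or Visit 8) and the end of safety follow-up.

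- For women who exit at Visit 2 or at an on-drug recurrence, add to the calendar one remote safety contact after the last dose, and extend the EMR review named in Section 13 to the end of the Section 9 window. State what applies to a woman who recurs at V7.
- Report adverse events by on-drug and post-last-dose period, and flag those that start after new therapy. Record the start date of that therapy.
- In the pregnancy text, clarify that leaving the study does not end safety follow-up.

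The cost is a wording amendment and one short contact for roughly 11 women plus the Visit 2 exits. The downside is weaker attribution of late events once other therapy has begun. EMR review will also miss mild events that never reach care, so the contact is needed as well. Where women have already exited without contact, only the chart review remains, and the report should say so.
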